Pharmacogenomic Analyses

Pharmacogenomic samples may be used for research related to pimodivir or influenza A. They may also be used to develop tests/assays related to pimodivir or influenza A. Pharmacogenomic research may consist of the analysis of one or more candidate genes or of the analysis of genetic markers throughout the genome or analysis of the entire genome (as appropriate) in relation to pimodivir clinical endpoints. Results of pharmacogenomic analysis will be reported in a separate report.

Pharmacokinetic Analyses

Population PK analysis of plasma concentration-time data of pimodivir will be performed using nonlinear mixed-effects modeling. Data may be combined with those of other selected studies (ie, Phase 1 and 2 studies) to support a relevant structural model. Available baseline subject characteristics (eg, demographics, body weight, laboratory variables, race, etc.) will be tested as potential covariates affecting PK parameters. The results of the population PK analysis will be reported in a separate report.

Pharmacokinetic/Pharmacodynamic Analyses

The PK/PD relationship of pimodivir exposure (area under the plasma concentration-time curve from time 0 to 12 hours after dosing [AUC_{12h}], maximum plasma concentration [C_{max}], or plasma concentration just prior to the beginning or at the end of a dosing interval [C_{trough}]) with selected efficacy (eg, time from start of study drug to hospital discharge, change in viral load from baseline and in other virologic response parameters) and safety (including AEs and laboratory abnormalities) parameters will be explored. If there is any visual trend in graphical analysis, suitable models will be applied to describe the exposure-effect relationships. Results of PK/PD analyses will be reported in a separate report.

Taste and Swallowability

Taste and swallowability questionnaire results (collected for adolescents who take pimodivir or placebo tablets; not applicable when tablets are administered via nasogastric tube) will be summarized per tablet intake (first and last intake of the study drug) by means of frequency tabulations. For overall taste, a dichotomization will be made for the overall question, categorizing 'bad' and 'almost acceptable' vs 'acceptable' and 'good'. For the swallowability, a dichotomization will be made of 'slightly difficult' or worse vs 'neither difficult nor easy' or better. The number of subjects (%) will be presented by category.

Safety Analyses

All safety endpoints will be evaluated on the Safety population, consisting of all subjects who received at least one dose of study drug and will be analyzed by actual treatment received. Safety will be evaluated by means of AEs, clinical laboratory tests, ECGs, vital signs, peripheral capillary oxygen saturation, and (symptom-directed) physical examinations. The safety analysis will be performed for each study phase separately (treatment, treatment extension, follow-up, and combined). Descriptive statistics and frequency tabulations will be provided.

Interim Analysis

An interim analysis will be implemented to assess lack of efficacy in the subgroup with time since onset of influenza symptoms between 72 and 96 hours. This interim analysis will be implemented through an IDMC, providing recommendations to a Sponsor Committee. Only the IDMC and the independent statistical support group will be unblinded to the data.

- In case lack of efficacy is concluded for the subgroup with time since onset of influenza symptoms between 72 and 96 hours:
 - Enrollment in this subgroup will be stopped.

-
- Sample size re-estimation will be performed based on the subgroup with time since onset of influenza symptoms ≤ 72 hours and consequently, the sample size of this subgroup may be increased. The maximum number of subjects that may be enrolled in this subgroup will be approximately 900.
 - Futility will be assessed in the subgroup with time since onset of influenza symptoms ≤ 72 hours based on re-estimated sample size.
 - At the final analysis, hypotheses will be evaluated in the subgroup with time since onset of influenza symptoms ≤ 72 hours.
 - In case no lack of efficacy is concluded for the subgroup with time since onset of influenza symptoms between 72 and 96 hours:
 - The subgroup with time since onset of influenza symptoms between 72 and 96 hours will be continued in the study.
 - Sample size re-estimation will be performed based on all subjects. The sample size may be increased. The maximum total number of subjects that may be enrolled in the study will be approximately 900. The study population should consist of at least 75% of subjects with first administration of study drug ≤ 72 hours since onset of influenza symptoms.
 - Futility will be assessed in all subjects based on re-estimated sample size.
 - At the final analysis, hypotheses will be evaluated in all subjects.

Details on the statistical decision rules will be provided in a separate Modeling and Simulation Report. The interim analysis will be conducted at the end of the first influenza season when between 300 and 450 subjects have been enrolled or during the season when 450 subjects have been enrolled. Further details will be specified in the IDMC charter.

TIME AND EVENTS SCHEDULES

1. TIME AND EVENTS SCHEDULE – DURING HOSPITALISATION (UP TO DISCHARGE)

Phase	Screening / Baseline	Treatment ^a					Follow-up ^a					
		Day	0-1 ^b	1	2	3	4	5	6	7-13	14	15-27
Screening/Administrative/Safety												
ICF/assent form	X											
Inclusion/exclusion criteria	X ^c											
Medical and surgical history, demographics, influenza vaccination status, substance use	X											
Physical exam	X											X
Symptom-directed physical exam		1x daily until discharge or through Day 14 (whichever comes first)										
Height and weight ^d	X											
12-lead ECG ^e	X											X
Pregnancy test (female subjects of childbearing potential)	X ^f			X								X
Treatment extension criteria ^g						X						
Randomization/Administration												
Randomization	X											
Administration of study drug		X ^h	X	X	X	X ^h						
Virology												
Nasal swab for local virology testing ⁱ	X ^j											
Nasal MT swab for central testing ^k	X		X	X ^l	X	X ^l		X	X			
Endotracheal aspirate (only if intubated) ^k	X		X	X ^l	X	X ^l		X	X			
Efficacy/Safety												
Vital signs/pulse oximetry ^m	X ⁿ	3x daily until discharge or through Day 14 (whichever comes first) ^o										X
Level of consciousness by ACVPU	X ⁿ	3x daily until discharge or through Day 14 (whichever comes first) ^o										X
Influenza Symptom Diary ^{z,aa}	X	2x daily from Day 2 through the Final Study Visit/Safety Follow-up Visit										
Assessment of daily activities resumption ^{p,aa}	X	1x daily from Day 2 through the Final Study Visit/Safety Follow-up Visit										
PGIS ^{q,aa}	X	1x daily from Day 2 through the Final Study Visit/Safety Follow-up Visit										
PGIC ^{r,aa}							X		X			X
EQ-5D ^{s,aa}	X						X		X			X
Hematology, chemistry	X ^{t,u}			X ^u			X ^u		X ^u			X ^u
Urinalysis	X			X			X		X			X

Phase	Screening / Baseline	Treatment ^a					Follow-up ^a				
Day	0-1 ^b	1	2	3	4	5	6	7-13	14	15-27	28 Safety Follow-up Visit / Final Study Visit ^a
Pharmacokinetics ^v		X		X ^l		X ^l					
Blood biomarker sampling (host RNA) ^w	X			X							
Pharmacogenomic sampling (host DNA) ^{w,x}				X							
Taste and swallowability		X ^y				X ^y					
Adverse events recording	X	X	X	X	X	X	X	X	X	X	X
Prestudy and concomitant medication recording	X	X	X	X	X	X	X	X	X	X	X
Assessment of readiness for hospital discharge		1x daily until discharge or through Final Study Visit/Safety Follow-up Visit (whichever comes first)									
Assessment of ICU level of care requirement		1x daily while in the ICU or through Final Study Visit/Safety Follow-up Visit (whichever comes first)									

Abbreviations: ACVPU: alert, new confusion, voice, pain, unresponsive; DNA: deoxyribonucleic acid; EQ-5D: European Quality of Life 5 Dimensions; ECG: electrocardiogram; ICF: informed consent form; MT: mid-turbinate; PGIC: Patient Global Impression of Change; PGIS: Patient Global Impression of Severity; RNA: ribonucleic acid.

- Subjects who prematurely discontinue study drug treatment for any reason (except withdrawal of consent) will be asked to continue with their remaining study visits and assessment schedule. Subjects who withdraw consent during the treatment or follow-up phase will be offered an optional Safety Follow-up Visit. The optional Safety Follow-up Visit will occur the day of consent withdrawal or the day after and will consist of the same assessments as at the Final Study Visit (Day 28), with optional patient-reported outcome (PRO) completion.
- Screening/baseline assessments start at signing of the ICF/assent form and can continue the next calendar day if needed. All screening/baseline procedures should take place prior to the first study drug intake.
- Investigators should ensure that all study enrollment criteria have been met at screening. If a subject's clinical status changes (including any available laboratory results or receipt of additional medical records) after screening but before the first dose of study drug is given such that they no longer meet all eligibility criteria, they should be excluded from participation in the study.
- Height and body weight are only to be measured at screening if not already available in the subject's chart and if practically feasible.
- Subjects should rest in a supine position for at least 5 minutes before ECG collection and should refrain from talking or moving arms or legs. If blood sampling or vital signs measurement is scheduled for the same time point as ECG recording, the procedures should be performed in the following order: ECGs, vital signs, blood draw. An ECG recorded within 1 calendar day before signing of the ICF/assent form can be used in lieu of the baseline ECG requirement.
- The result of a prior pregnancy test (urine or serum) that occurred within 1 calendar day before signing of the ICF/assent form can be used in lieu of the baseline requirement.
- Subjects who meet the treatment extension criteria and agree to participate in the treatment extension arm, should be switched to the **3. TIME AND EVENTS SCHEDULE – DURING HOSPITALIZATION (UP TO DISCHARGE), FOR PATIENTS WHO ENTERED THE OPTIONAL DOUBLE-BLIND EXTENSION TREATMENT ARM** on Day 6, and then switched to the **4. TIME AND EVENTS SCHEDULE – AFTER DISCHARGE FROM HOSPITAL, FOR PATIENTS WHO HAD ENTERED THE OPTIONAL DOUBLE-BLIND EXTENSION TREATMENT ARM** after discharge from hospital.

-
- h. Depending on the time of screening/enrollment, subjects will receive 1 dose (evening) or 2 doses (morning and evening) of study drug on Day 1. For subjects who receive only 1 dose of pimodivir or placebo on Day 1 (evening), dosing should continue until the morning of Day 6 so that all subjects receive 10 doses in total.
 - i. Polymerase chain reaction (PCR)-based or other rapid molecular diagnostic assay performed locally. It is recommended to use MT swabs for local virology testing, although nasopharyngeal (NP) swabs are allowed if required by local procedures. Nasal swabs for local virology testing should be obtained from the left and right nostrils (from both nostrils if feasible, but from only one nostril otherwise) and pooled into the same collection tube. If available, leftovers from the local virology sample (with the exception of “an earlier sample”, see footnote j) will be shipped to and stored at the central lab for further testing, regardless of local influenza test result.
 - j. The results of an earlier sample collected and tested positive for influenza A infection after the onset of symptoms using a PCR-based or other rapid molecular diagnostic assay can be used in lieu of the local virology testing at screening. This sample is used to determine eligibility.
 - k. Central virology testing: Nasal MT swabs should be obtained from the left and the right nostrils (from both nostrils if feasible, but from only one nostril otherwise) and pooled into the same collection tube. In case the subject is intubated, endotracheal samples should be taken as well, at the same time as the nasal MT swab. The samples will be collected at screening/baseline and on Days 2, 3, 4, 5, 8, 10, and 14. The screening/baseline sample needs to be collected predose, as close as possible to the first dose. Sampling should be done at approximately the same time (± 4 hours) on each sampling day. Leftovers from nasal MT swabs and endotracheal samples collected for virology testing may be used for protein biomarker analysis, if not restricted by local regulations.
 - l. At the time points where both nasal MT swabs/endotracheal aspirate and pharmacokinetic (PK) samples are obtained, these samples should be obtained as close together in time as possible.
 - m. Vital signs include body temperature, pulse rate, respiratory rate, and blood pressure. For peripheral capillary oxygen saturation, it should be recorded whether the measurement was with or without supplemental oxygen. The SpO₂ should be measured either in a sitting or supine position after 5 minutes of rest in a quiet environment.
 - n. National Early Warning Score (NEWS2) should be calculated before randomization as NEWS2 at baseline is an inclusion criterion (≥ 4) as well as a stratification factor (4-5 or >5).
 - o. Vital signs/peripheral capillary oxygen saturation (pulse oximetry)/ACVPU are to be evaluated 3 times daily: in the morning (prior to study drug intake if applicable), approximately half-way in the middle of the day, and in the evening (prior to study drug intake if applicable).
 - p. Questionnaire (Return to daily activities) to be completed at screening/baseline (as close as possible to the first dose) and then once daily onto the ePRO device.
 - q. Questionnaire (PGIS) to be completed at screening/baseline (as close as possible to the first dose) and then once daily onto the ePRO device.
 - r. Questionnaire (PGIC) to be completed on Days 6, 14, and 28 onto the ePRO device.
 - s. Questionnaire (EQ-5D) to be completed at screening/baseline (as close as possible to the first dose) and on Days 6, 14, and 28 onto the ePRO device.
 - t. Follicle-stimulating hormone (FSH) will be tested at screening for female subjects who are amenorrheic for 12 months or less.
 - u. If feasible, safety blood samples will be collected after fasting for at least 10 hours.
 - v. Sparse PK sampling will be performed as follows (during hospitalization):
 - On Day 1: between 1.5 and 6 hours after the morning or evening dose (preferably the morning dose).
 - On Day 3: predose (≤ 1 hour prior to morning or evening dose).
 - On Day 5: predose (≤ 1 hour prior to dosing) and between 1.5 and 6 hours after the dose. Either the morning or evening dose (whichever is the most convenient) can be considered for this sampling.Leftovers from samples collected for PK testing may be used for protein biomarker analysis, if not restricted by local regulations.
 - w. If not restricted by local regulations.
 - x. This pharmacogenomic sample collection is optional. The pharmacogenomic sample should preferably be collected at the specified time point, however if necessary it may be collected at another time point without constituting a protocol deviation.

- y. The taste and swallowability questionnaire for pimodivir or placebo should only be completed by adolescent subjects. The questionnaire should be completed within approximately 15 minutes after the first and last pimodivir or placebo intake (not applicable when tablets are administered via nasogastric tube). For subjects who receive the last dose of pimodivir or placebo on Day 6 (see footnote [h](#)), the questionnaire should be completed on Day 6.
- z. Influenza symptom diary to be completed at screening/baseline (prior to the first dose) and then twice daily onto the ePRO device.
- aa. PRO assessments will be completed by all subjects at sites where appropriate PROs and translations are available and approved.

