2. TIME AND EVENTS SCHEDULE – AFTER DISCHARGE FROM HOSPITAL

Note: This Time and Events Schedule should start with the study day number following the day of discharge from the hospital (for example: subjects discharged on Study Day 3 would start with Day 4 procedures on this schedule). After subjects are discharged, the remainder of the study visits should be carried out as outpatient visits (preferably on-site or, if not feasible, at the subject's home) or by telephone follow-up as indicated in the table below. Every effort should be made to perform all of the assessments as outlined below (either on-site or at the subject's home), if practically feasible. In case of readmission to the hospital, subjects will continue to follow this Time and Events Schedule until the end of the study.

Phase Day	Treatment ^{a,b} 2/3/4/5	Follow-up ^b						
		6 ^c	7-9	10 +/-1 Day	11-13	14 +/-1 Day	15-27	28 +/-1 Day
	Phone Follow-up ^e						Phone Follow-up ^f	Safety Follow-up Visit / Final Study Visit ^b
Clinic or home visit		X		X		X		X
Administration								
Administration of study drug ^{a,g}	X							
Virology								
Nasal MT swab for central testing ^h		X ⁱ		X		X		
Efficacy/Safety								
Vital signs/pulse oximetry ^j		X						X
Physical exam								X
Symptom-directed physical exam		X		X		X		
12-lead ECG ^k								X
Pregnancy test (female subjects of childbearing potential)	X ^l							X
Influenza Symptom Diary ^{s,t}		2x daily through the Final Study Visit/Safety Follow-up Visit ^d						
Assessment of daily activities resumption ^{m,t}		1x daily through the Final Study Visit/Safety Follow-up Visit ^d						
PGIS ^{n,t}		1x daily through the Final Study Visit/Safety Follow-up Visit ^d						
PGIC ^{o,t}		X ^d				X ^d		X
EQ-5D ^{p,t}		X ^d				X ^d		X
Hematology, chemistry		X ^q				X ^q		X ^q
Urinalysis		X				X		X
Pharmacokinetics		X ⁱ						
Taste and swallowability	X ^r							
Adverse events recording	X	X		X		X	X	X
Prestudy and concomitant medication recording	X	X		X		X	X	X

Abbreviations: ECG: electrocardiogram; EQ-5D: European Quality of Life 5 Dimensions; MT: mid-turbinate; PGIC: Patient Global Impression of Change; PGIS: Patient Global impression of Severity.

- a. If the subject is discharged during study treatment, he/she will receive study drug for at-home use.

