- t. PRO assessments will be completed by all subjects at sites where appropriate PROs and translations are available and approved.

3. TIME AND EVENTS SCHEDULE – DURING HOSPITALIZATION (UP TO DISCHARGE), FOR PATIENTS WHO ENTERED THE OPTIONAL DOUBLE-BLIND EXTENSION TREATMENT ARM

Note: This Time and Events Schedule is only applicable for hospitalized patients who entered the treatment extension phase (see Sections 4.3 and 9.1.4 for eligibility criteria), and should be followed up to discharge.

Phase Day	Optional Extended Blinded Treatment ^a					Follow-up ^a						
	6	7	8	9	10	11	12-13	14	15-18	19	20-32	33 Safety Follow-up Visit / Final Study Visit ^a
Administration												
Administration of study drug ^b	X	X	X	X	X							
Virology												
Nasal MT swab for central testing ^c	X	X	X	X	X			X		X		
Endotracheal aspirate (only if intubated) ^e	X	X	X	X	X			X		X		
Efficacy/Safety												
Vital signs/pulse oximetry ^d	3x daily until discharge or through Day 19 (whichever comes first) ^e											X
Level of consciousness by ACVPU	3x daily until discharge or through Day 19 (whichever comes first) ^e											X
Physical exam												X
Symptom-directed physical exam	1x daily until discharge or through Day 19 (whichever comes first)											
12-lead ECG ^f												X
Pregnancy test (female subjects of childbearing potential)			X									X
Influenza Symptom Diary ^{l,m}	2x daily through the Final Study Visit/Safety Follow-up Visit											
Assessment of daily activities resumption ^{g,m}	1x daily through Final Study Visit/Safety Follow-up Visit											
PGIS ^{h,m}	1x daily through Final Study Visit/Safety Follow-up Visit											
PGIC ^{i,m}	X							X		X		X
EQ-5D ^{j,m}	X							X		X		X
Hematology, chemistry			X ^k			X ^k				X ^k		X ^k
Urinalysis			X			X				X		X
Adverse events recording	X	X	X	X	X	X	X	X	X	X	X	X
Prestudy and concomitant medication recording	X	X	X	X	X	X	X	X	X	X	X	X
Assessment of readiness for hospital discharge	1x daily until discharge or through Final Study Visit/Safety Follow-up Visit (whichever comes first)											
Assessment of ICU level of care requirement	1x daily until discharge or through Final Study Visit/Safety Follow-up Visit (whichever comes first)											

Abbreviations: ACVPU: alert, new confusion, voice, pain, unresponsive; ECG: electrocardiogram; EQ-5D: European Quality of Life 5 Dimensions; MT: mid-turbinate; PGIC: Patient Global Impression of Change; PGIS: Patient Global impression of Severity.

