Once daily, an assessment of readiness for discharge and ICU level of care requirement will be performed.

Subjects, who are discharged during the treatment phase, will receive study drug for at-home use.

End of Treatment

A subject will be considered to have completed treatment after 5-day therapy of pimodivir or placebo (ie, 10 doses).

Subjects (1) who complete the 5-day treatment, (2) who are still hospitalized upon treatment completion, (3) who are on invasive mechanical ventilation or who have an ongoing respiratory deficiency as evidenced by having an SpO₂ <94% on room air, or in case of known pre-influenza SpO₂ <94% (eg, due to COPD), the current blood oxygen saturation on room air is lower than pre-influenza infection levels by at least 3%, (4) who, in the opinion of the investigator, are expected to derive clinical benefit from extending the treatment period, and (5) for whom the investigator agrees to extend treatment with the same SOC will be given the option for treatment extension. In the second blinded course of treatment, subjects will continue treatment with pimodivir or placebo for another 5 days in combination with continued SOC treatment. If the SOC contained no influenza antiviral during the first treatment period, no influenza antiviral can be started in the treatment extension as part of the SOC (see Section 9.1.4).

Early Withdrawal

Subjects who prematurely discontinue study drug treatment for any reason (except withdrawal of consent) will be asked to continue with their remaining study visits and assessment schedule. Subjects who withdraw consent during the treatment phase will be offered an optional Safety Follow-up Visit. The optional Safety Follow-up Visit will occur the day of consent withdrawal or the day after and will consist of the same assessments as at the Final Study Visit (Day 28 or Day 33), with optional PRO completion. If the subject discontinues treatment due to an AE or other medical reason, efforts will be made by the investigator to continue following up with the subject at regular intervals until the AE normalizes or returns to the subject's baseline condition. The sponsor and the investigator will agree on an acceptable individual follow-up schedule for these subjects.

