9.1.5. Post-treatment Phase (Follow-up)

The procedures to be completed during the follow-up phase are listed in the [TIME AND EVENTS SCHEDULES](#).

Subjects who withdraw consent during the follow-up phase will be offered an optional Safety Follow-up Visit. The optional Safety Follow-up Visit will consist of the same assessments as at the Final Study Visit (Day 28 or Day 33), with optional PRO completion. In case of ongoing AEs, efforts will be made by the investigator to continue following up with the subject at regular intervals until the AE normalizes or returns to the subject's baseline condition.

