9.2. Efficacy

9.2.1. Evaluations

9.2.1.1. Hospital Recovery Scale Assessment

The hospital recovery scale assesses a subject's clinical status and will be assessed as the subject's condition on Day 6 as the primary endpoint. The hospital recovery scale will be assessed on Days 2 to 14 (excluding the primary time point) as secondary endpoints.

The hospital recovery scale provides 6 mutually exclusive conditions ordered from best to worst, and the score reflects the subject's worst situation on the day of assessment:

1. Not Hospitalized
2. Non-ICU Hospitalization, Not Requiring Supplemental Oxygen
3. Non-ICU Hospitalization, Requiring Supplemental Oxygen
4. Admitted to the ICU, Not Requiring Invasive Mechanical Ventilation
5. Requiring Invasive Mechanical Ventilation
6. Death

The hospital recovery scale categories are defined below. For ease of categorization, the categories are defined from worst to best.

Hospital Recovery Scale: Definitions^a

6. Death
 - Subject died at any time on the day of assessment or earlier (all-cause mortality).
5. Requiring invasive mechanical ventilation
 - Any oxygen support requiring intubation or extracorporeal oxygenation
 - Invasive mechanical ventilation is used at any time on the day of assessment.
4. Admitted to the ICU, not requiring invasive mechanical ventilation
 - Subject met either of the 2 following criteria:
 - In the ICU (and ICU level of care is required during the day of assessment)
 - On the hospital ward, with or without supplemental oxygen, but deemed to require ICU level of care at any time during the day of assessment (eg, not transferred to ICU due to bed availability)
 - Requiring ICU level of care is defined by:
 - Some specific conditions:
 - Treatment of acute unstable arrhythmias
 - Treatment of complicated acid-base or electrolyte imbalances
 - Large volume resuscitation
 - Utilization of intravenous vasoactive medications

^a If a subject was discharged from the hospital “Against Medical Advice” on the day prior to the day of assessment, the subject will be categorized per the definitions above in the category the subject was in at the moment of discharge “Against Medical Advice”. The hospital recovery scale category will be considered missing on subsequent days.

If a subject declines medically-indicated mechanical ventilation or care that requires an ICU level of intervention, the subject will be categorized according to the care they would otherwise have received on that day.

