5.2.2. Estimand

The population of interest is hospitalized subjects between 13 to 85 years old with a confirmed influenza A infection.

The primary variable is the hospital recovery scale as assessed on Day 6 and will be compared between pimodivir and placebo on top of SOC. The hospital recovery scale is an ordinal mutually exclusive scale of six categories (death, requiring mechanical ventilation, requiring ICU, non-ICU hospitalized requiring supplemental oxygen, non-ICU hospitalized not requiring supplemental oxygen and non-hospitalized).

The intercurrent event of the use of influenza antivirals as part of SOC is handled in a treatment policy strategy as the primary endpoint is derived in the same way irrespective of the components of SOC. Treatment discontinuation is an intercurrent event that is also handled in a treatment policy strategy. Death as intercurrent event is handled in a composite strategy as it is one of the categories of the HRS. Other factors as for example bed availability that can influence the status of the subject are intercurrent events that are also handled with the composite strategy as the HRS accounts for the status of where the subject ‘should be’ instead of where the subject physically is.

The common odds ratio estimated by a proportional odds model is used as the population-level summary. If the assumption (by testing the parallel slopes for the treatment effect only) of the proportional odds would not hold for the treatment effect, the Van Elteren test will be used in a sensitivity analysis and the resulting p-value would be used in the formal testing. A second sensitivity analysis is conducted to handle missing data by an MAR/MNAR multiple imputations method. This is done for all missing HRS values on day 6 and separately for HRS values on day 6 that are missing due to COVID-19 and for HRS values that are missing not due to COVID-19.

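### Schedule 1 limits the daily ICU level-of-care assessment to days in the ICU, against Section 9.1.3, Schedule 3 and recovery-scale category 4; readmission days also lack scheduled inputs to the scale

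*Protocol*

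**What the plan says.** Protocol Section 9.2.1.1 puts in category 4 not only patients in the ICU but also those on the ward, "but deemed to require ICU level of care at any time during the day of assessment (eg, not transferred to ICU due to bed availability"). SAP Section 5.2.1 repeats this. SAP Section 5.2.2 relies on it for bed shortage, saying that "the HRS accounts for the status of where the subject ‘should be’ instead of where the subject physically is".

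The instructions for collecting the judgement of ICU need differ:

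- Time and Events Schedule 1 (in hospital, no extension): "1x daily while in the ICU or through Final Study Visit/Safety Follow-up Visit (whichever comes first").
- Section 9.1.3 (treatment phase): "Once daily, an assessment of readiness for discharge and ICU level of care requirement will be performed".
- Time and Events Schedule 3 (in hospital, extension, from Day 6): "1x daily until discharge or through Final Study Visit/Safety Follow-up Visit (whichever comes first").

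For the follow-up phase, Section 9.1.5 adds no instruction of its own: "The procedures to be completed during the follow-up phase are listed in the" Time and Events Schedules.

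Readmitted patients have a rule of their own in Schedule 2, repeated in Schedule 4: "In case of readmission to the hospital, subjects will continue to follow this Time and Events Schedule until the end of the study". Neither schedule has a row for discharge readiness or ICU level of care. Oximetry is listed on Day 6 (Day 7 is allowed) and Day 28 in Schedule 2, and on Day 11 (Day 12 is allowed) and Day 33 in Schedule 4. Yet HRS categories 2 and 3 expressly include readmittance.

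**The concern.** A scale meant to record where the patient ought to be needs a daily judgement of ICU need for patients who are not in the ICU. Under the Schedule 1 row as written, the ward part of category 4 has no scheduled input. On Day 6 extended patients are assessed daily on the ward while non-extended patients are not, and extension is decided after randomization.

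The readmission rule leaves a second gap. On readmission days the scale needs readiness, ICU need and oxygen status, and the schedules that apply ask for almost none of them.

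The stake is whether the primary endpoint (Day 6), the secondary HRS days and time to clinical failure (defined in SAP Section 5.3.1.1 as HRS above 3) measure what the SAP says they measure.

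**Working it through.** **1. Which instruction governs which day, for a non-extended ward patient.** On the treatment days Section 9.1.3 and the Schedule 1 row contradict each other. Schedule 1 places Day 6 and later in follow-up, and Section 9.1.5 sends the site back to that schedule, so only the restrictive row remains. Patients who start in the evening take their tenth dose on the morning of Day 6, so Section 9.1.3 arguably still reaches them that day. Discharge readiness (daily) and vital signs with oximetry ("3x daily until discharge or through Day 14 (whichever comes first")) are scheduled on the ward. Only the ICU-need item is affected.

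**2. What Attachment 6 does when an item is absent.**

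| Situation | Score | Direction |
|---|---|---|
| Ward, neither REQICU nor REASICU recorded | 3 or 2; category 4 needs a 'Y' | Too good if ICU care is needed |
| ICU, both items missing | 4, unless ready for discharge on that day and the day before | Not too good |
| Readiness missing | Not released to category 1 | Possibly too poor |
| On oxygen, not chronic, VSOXYSAT missing | 3 by the code and example Case 1; Case 7 says oxygen is not required, hence 2 | Contradictory |
| Off oxygen, no SpO2 record | 2 | Too good if hypoxic |

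**3. Timing of readmission.** Attachment 6 requires a day between the two stays. A re-hospitalization starting on Day 6 therefore implies discharge by Day 4. This limb bears mainly on Days 7 to 14.

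**4. The plan's own figure.** Inputs from Protocol Section 11.3 are the placebo distribution 30/30/25/5/5/5%, odds ratio 1 − 0.38 = 0.62, 1:1 allocation and 90% power. The two-sided 5% level is from Section 11.4. Whitehead's formula is N = 12(z₁ + z₂)² / {(ln OR)² [1 − Σp̄³]}, where p̄ is the mean of the two arms' category probabilities. The pimodivir distribution is 40.87/29.88/19.38/3.42/3.28/3.16%, which gives Σp̄³ ≈ 0.0825.

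N = 12 × (1.960 + 1.282)² / (0.2285 × 0.9175) ≈ 601, and power at 600 is 89.9%. The plan's figures are reproduced.

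**5. Size on Day 6 under an assumption.** Expected category 4 counts are 300 × 5% = 15 on placebo and 300 × 3.42% = 10.3 on pimodivir. The documents give no ward share. If 10% to 50% were on a ward with no record, 1.5 to 7.5 placebo and 1.0 to 5.1 pimodivir patients would be misplaced.

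**6. Effect on the analysis.** True category 4 is moved to category 3, and power is from a likelihood-ratio calculation whose starting value is 89.7%.

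| Category 4 lost | Odds ratio | Power |
|---|---|---|
| 10% to 90%, both arms | 0.62 | 89.7% to 89.5% |
| 25% to 50%, placebo only | 0.626 to 0.631 | 88.5% to 87.3% |
| 25% to 50%, pimodivir only | 0.614 to 0.609 | 90.7% to 91.6% |

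The one-arm rows are bounds for illustration. The documents give no reason to expect them.

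**The case against.** The best reply is that the item is in fact called for on the ward. Section 9.1.3 and Schedule 3 both ask for it, Attachment 6 has a ward branch that reads it, and the eCRF, which settles what sites record, is not among the documents. This stands: it is a contradiction to reconcile, and a reader who inferred that the data do not exist would go further than the text. It does not dispose of the point, because from Day 6 the text defers to the restrictive row.

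Second, extension requires continuing hospitalization with invasive ventilation or respiratory deficiency, so many of the ward patients most at risk may be on Schedule 3 on Day 6. This narrows the gap. But extension is optional and rests partly on the investigator's opinion, and several ICU-level conditions listed in Section 9.2.1.1 are not respiratory.

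Third, a reader might infer that severe outcomes are systematically under-scored. Attachment 6 does not support that: missing readiness holds patients in a worse category, and ICU stays default to 4. For SpO2, Protocol Section 9.6.4 has additional routine vital signs entered in the eCRF, which partly fills the readmission gap. SAP Section 2.1.5 excludes unscheduled values from per-time-point analyses but uses them for worst-case determination, and it is unclear which rule applies to the HRS. Neither provision supplies readiness or ICU need.

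Fourth, the fundamental HRS (SAP Section 5.3.1.1) follows actual location and does not use these judgements. It is a useful cross-check but by design does not count ICU need on the ward.

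**Conclusion.** The Schedule 1 row contradicts Section 9.1.3, Schedule 3 and the category 4 definition. It takes effect on Day 6, where a non-extended ward patient (arguably except evening starters) has no scheduled ICU-need record and would be scored 3 or 2 instead of 4. Readmitted patients lack scheduled readiness and ICU-level records and have sparse oximetry. That affects mainly the secondary Day 7 to 14 scores, and the direction is mixed.

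One might infer from the link with extension status that the treatment comparison is biased. The documents do not show that: treatment is double-blind, no mechanism for different loss by arm is described, and equal proportional loss leaves the odds ratio at 0.62 and power at 89.5% or more. The sample size stands. What is at issue is whether part of the primary endpoint is measured as the estimand states. The counts rest on an assumed ward share of 10% to 50% and on every such patient lacking a record; no rate is given for ward or readmitted patients.

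**What to change.** - Give the Schedule 1 ICU level-of-care row the Schedule 3 wording, so that it runs daily until discharge or the final visit and agrees with Section 9.1.3.
- In Schedules 2 and 4, have discharge readiness, ICU level of care and pulse oximetry recorded on readmission days up to Day 14 (Day 19 if extended).
- In Attachment 6, state a missing-value rule for the ward branch of category 4, and reconcile example Case 1 with Case 7.

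The cost is one daily eCRF item for ward inpatients, transcription of routine observations for the readmitted patients (probably few), and edits to the protocol tables and the SAP attachment. Treatment, sample size and the analysis model do not change.
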